## **7. DATA COLLECTION AND MANAGEMENT**

### **7.1 DATA QUALITY ASSURANCE**

The Sponsor will be responsible for data management of this study, including quality checking of the data. Data entered manually will be collected via EDC through use of eCRFs. Sites will be responsible for data entry into the EDC system. In the event of discrepant data, the Sponsor will request data clarification from the sites, which the sites will resolve electronically in the EDC system.

The Sponsor will produce an EDC Study Specification document that describes the quality checking to be performed on the data. Data will be sent directly to the Sponsor, using the Sponsor's standard procedures to handle and process the electronic transfer of these data.

eCRFs and correction documentation will be maintained in the EDC system's audit trail. System backups for data stored by the Sponsor and records retention for the study data will be consistent with the Sponsor's standard procedures.

PRO data, other than the data obtained from Question 3 of the BPI-SF at screening, will be collected through the use of an electronic device provided by a vendor. For situations that preclude the use of the electronic device, a backup paper option may be utilized. The device is designed for entry of data in a way that is attributable, secure, and accurate, in compliance with FDA, regulations for electronic records (21 CFR Part 11). The electronic data are available for view access only via secure access to a vendor hosted, password protected web portal. Only identified and trained users may view the

data, and their actions become part of the audit trail. The Sponsor will have view access only. System backups for data stored by the Sponsor and records retention for the study data will be consistent with the Sponsor's standard procedures.

## **7.2 ELECTRONIC CASE REPORT FORMS**

eCRFs are to be completed through use of a Sponsor-designated EDC system. Sites will receive training and have access to a manual for appropriate eCRF completion. eCRFs will be submitted electronically to the Sponsor and should be handled in accordance with instructions from the Sponsor.

All eCRFs should be completed by designated, trained site staff. eCRFs should be reviewed and electronically signed and dated by the investigator or a designee.

At the end of the study, the investigator will receive patient data for his or her site in a readable format that must be kept with the study records. Acknowledgement of receipt of the data is required.

## **7.3 ELECTRONIC PATIENT-REPORTED OUTCOME DATA**

An electronic device will be used to capture PRO data at the site visit and at home between study visits. It is critical that patients are reminded to bring their provisioned electronic device at each visit. The data will be transmitted to a centralized database maintained by the electronic device vendor. Once the study is complete, the data, audit trail, and study and system documentation will be archived. The investigator will receive patient data for the site in both human and machine-readable formats on an archival-quality compact disc that must be kept with the study records as source data. Acknowledgement of receipt of the compact disc is required. In addition, the Sponsor will receive all data in a machine-readable format.

## **7.4 SOURCE DATA DOCUMENTATION**

Study monitors will perform ongoing source data verification and review to confirm that critical protocol data (i.e., source data) entered into the eCRFs by authorized site personnel are accurate, complete, and verifiable from source documents.

Source documents (paper or electronic) are those in which patient data are recorded and documented for the first time. They include, but are not limited to, hospital records, clinical and office charts, laboratory notes, memoranda, PROs, evaluation checklists, pharmacy dispensing records, recorded data from automated instruments, copies of transcriptions that are certified after verification as being accurate and complete, microfiche, photographic negatives, microfilm or magnetic media, X-rays, patient files, and records kept at pharmacies, laboratories, and medico-technical departments involved in a clinical study.

Before study initiation, the types of source documents that are to be generated will be clearly defined in the Trial Monitoring Plan. This includes any protocol data to be

entered directly into the eCRFs (i.e., no prior written or electronic record of the data) and considered source data.

Source documents that are required to verify the validity and completeness of data entered into the eCRFs must not be obliterated or destroyed and must be retained per the policy for retention of records described in Section 7.6.

To facilitate source data verification and review, the investigators and institutions must provide the Sponsor direct access to applicable source documents and reports for study-related monitoring, Sponsor audits, and IRB/EC review. The study site must also allow inspection by applicable health authorities.

## **7.5 USE OF COMPUTERIZED SYSTEMS**

When clinical observations are entered directly into a study site's computerized medical record system (i.e., in lieu of original hardcopy records), the electronic record can serve as the source document if the system has been validated in accordance with health authority requirements pertaining to computerized systems used in clinical research. An acceptable computerized data collection system allows preservation of the original entry of data. If original data are modified, the system should maintain a viewable audit trail that shows the original data as well as the reason for the change, name of the person making the change, and date of the change.

## **7.6 RETENTION OF RECORDS**

Records and documents pertaining to the conduct of this study and the distribution of IMP, including eCRFs, electronic or paper PRO data, Informed Consent Forms, laboratory test results, and medication inventory records, must be retained by the Principal Investigator for at least 15 years after completion or discontinuation of the study or for the length of time required by relevant national or local health authorities, whichever is longer. After that period of time, the documents may be destroyed, subject to local regulations.

No records may be disposed of without the written approval of the Sponsor. Written notification should be provided to the Sponsor prior to transferring any records to another party or moving them to another location.

## **8. ETHICAL CONSIDERATIONS**

### **8.1 COMPLIANCE WITH LAWS AND REGULATIONS**

This study will be conducted in full conformance with the ICH E6 guideline for Good Clinical Practice and the principles of the Declaration of Helsinki, or the laws and regulations of the country in which the research is conducted, whichever affords the greater protection to the individual. The study will comply with the requirements of the ICH E2A guideline (Clinical Safety Data Management: Definitions and Standards for Expedited Reporting). Studies conducted in the United States or under a U.S.

Investigational New Drug (IND) Application will comply with U.S. FDA regulations and applicable local, state, and federal laws. Studies conducted in the European Union or European Economic Area will comply with the E.U. Clinical Trial Directive (2001/20/EC).

## **8.2 INFORMED CONSENT**

The Sponsor's sample Informed Consent Form (and ancillary sample Informed Consent Forms such as a Child's Informed Assent Form or Mobile Nursing Informed Consent Form, if applicable) will be provided to each site. If applicable, it will be provided in a certified translation of the local language. The Sponsor or its designee must review and approve any proposed deviations from the Sponsor's sample Informed Consent Forms or any alternate consent forms proposed by the site (collectively, the "Consent Forms") before IRB/EC submission. The final IRB/EC-approved Consent Forms must be provided to the Sponsor for health authority submission purposes according to local requirements.

If applicable, the Informed Consent Form will contain separate sections for any optional procedures. The investigator or authorized designee will explain to each patient the objectives, methods, and potential risks associated with each optional procedure. Patients will be told that they are free to refuse to participate and may withdraw their consent at any time for any reason. A separate, specific signature will be required to document a patient's agreement to participate in optional procedures. Patients who decline to participate will not provide a separate signature.

The Consent Forms must be signed and dated by the patient or the patient's legally authorized representative before his or her participation in the study. The case history or clinical records for each patient shall document the informed consent process and that written informed consent was obtained prior to participation in the study.

The Consent Forms should be revised whenever there are changes to study procedures or when new information becomes available that may affect the willingness of the patient to participate. The final revised IRB/EC-approved Consent Forms must be provided to the Sponsor for health authority submission purposes.

Patients must be re-consented to the most current version of the Consent Forms (or to a significant new information/findings addendum in accordance with applicable laws and IRB/EC policy) during their participation in the study. For any updated or revised Consent Forms, the case history or clinical records for each patient shall document the informed consent process and that written informed consent was obtained using the updated/revised Consent Forms for continued participation in the study.

A copy of each signed Consent Form must be provided to the patient or the patient's legally authorized representative. All signed and dated Consent Forms must remain in each patient's study file or in the site file and must be available for verification by study monitors at any time.

For sites in the United States, each Consent Form may also include patient authorization to allow use and disclosure of personal health information in compliance with the U.S. Health Insurance Portability and Accountability Act (HIPAA) of 1996. If the site utilizes a separate Authorization Form for patient authorization for use and disclosure of personal health information under the HIPAA regulations, the review, approval, and other processes outlined above apply except that IRB review and approval may not be required per study site policies.

### **8.3 INSTITUTIONAL REVIEW BOARD OR ETHICS COMMITTEE**

This protocol, the Informed Consent Forms, any information to be given to the patient, and relevant supporting information must be submitted to the IRB/EC by the Principal Investigator and reviewed and approved by the IRB/EC before the study is initiated. In addition, any patient recruitment materials must be approved by the IRB/EC.

The Principal Investigator is responsible for providing written summaries of the status of the study to the IRB/EC annually or more frequently in accordance with the requirements, policies, and procedures established by the IRB/EC. Investigators are also responsible for promptly informing the IRB/EC of any protocol amendments (see Section 9.6).

In addition to the requirements for reporting all adverse events to the Sponsor, investigators must comply with requirements for reporting serious adverse events to the local health authority and IRB/EC. Investigators may receive written IND safety reports or other safety-related communications from the Sponsor. Investigators are responsible for ensuring that such reports are reviewed and processed in accordance with health authority requirements and the policies and procedures established by their IRB/EC, and archived in the site's study file.

### **8.4 CONFIDENTIALITY**

The Sponsor maintains confidentiality standards by coding each patient enrolled in the study through assignment of a unique patient identification number. This means that patient names are not included in data sets that are transmitted to any Sponsor location.

Patient medical information obtained by this study is confidential and may be disclosed to third parties only as permitted by the Informed Consent Form (or separate authorization for use and disclosure of personal health information) signed by the patient, unless permitted or required by law.

Medical information may be given to a patient's personal physician or other appropriate medical personnel responsible for the patient's welfare, for treatment purposes.

Given the complexity and exploratory nature of exploratory biomarker analyses, data derived from these analyses will generally not be provided to study investigators or patients unless required by law. The aggregate results of any conducted research will

be available in accordance with the effective Roche policy on study data publication (see Section 9.5).

Data generated by this study must be available for inspection upon request by representatives of national and local health authorities, Sponsor monitors, representatives, and collaborators, and the IRB/EC for each study site, as appropriate.

Study data, which may include data on germline mutations, may be submitted to government or other health research databases or shared with researchers, government agencies, companies, or other groups that are not participating in this study. These data may be combined with or linked to other data and used for research purposes, to advance science and public health, or for analysis, development, and commercialization of products to treat and diagnose disease. In addition, redacted clinical study reports and other summary reports will be provided upon request.

## **8.5 FINANCIAL DISCLOSURE**

Investigators will provide the Sponsor with sufficient, accurate financial information in accordance with local regulations to allow the Sponsor to submit complete and accurate financial certification or disclosure statements to the appropriate health authorities. Investigators are responsible for providing information on financial interests during the course of the study and for 1 year after completion of the study (i.e., receipt of the last data point required for the final analysis of the primary efficacy endpoint or sponsor decision to end the study, whichever occurs first).

## **9. STUDY DOCUMENTATION, MONITORING, AND ADMINISTRATION**

### **9.1 STUDY DOCUMENTATION**

The investigator must maintain adequate and accurate records to enable the conduct of the study to be fully documented, including, but not limited to, the protocol, protocol amendments, Informed Consent Forms, and documentation of IRB/EC and governmental approval. In addition, at the end of the study, the investigator will receive the patient data, including an audit trail containing a complete record of all changes to data.

### **9.2 PROTOCOL DEVIATIONS**

The investigator should document and explain any protocol deviations. The investigator should promptly report any deviations that might have an impact on patient safety and data integrity to the Sponsor and to the IRB/EC in accordance with established IRB/EC policies and procedures. The Sponsor will review all protocol deviations and assess whether any represent a serious breach of Good Clinical Practice guidelines and require reporting to health authorities. As per the Sponsor's standard operating procedures, prospective requests to deviate from the protocol, including requests to waive protocol eligibility criteria, are not allowed.

### **9.3 SITE INSPECTIONS**

Site visits will be conducted by the Sponsor or an authorized representative for inspection of study data, patients' medical records, and eCRFs. The investigator will permit national and local health authorities; Sponsor monitors, representatives, and collaborators; and the IRBs/ECs to inspect facilities and records relevant to this study.

### **9.4 ADMINISTRATIVE STRUCTURE**

This study will be sponsored and managed by F. Hoffmann-La Roche Ltd. Approximately 180 sites globally will participate in the study and approximately 730 patients will be enrolled.

Enrollment in the safety run-in and randomized phases of the study will occur through an IxRS system. In the randomized phase, randomization will be managed by IxRS. Central facilities will be used for study assessments throughout the study (e.g., specified laboratory tests, PK analyses, and medical imaging).

Accredited local laboratories will be used for routine monitoring; local laboratory ranges will be collected.

An iDMC will be convened to evaluate safety data during the study according to policies and procedures detailed in an iDMC Charter.

### **9.5 DISSEMINATION OF DATA AND PROTECTION OF TRADE SECRETS**

Regardless of the outcome of a study, the Sponsor is dedicated to openly providing information on the study to healthcare professionals and to the public, at scientific congresses, in clinical trial registries of the U.S. National Institutes of Health and the European Medicines Agency, and in peer-reviewed journals. The Sponsor will comply with all requirements for publication of study results. Study data may be shared with others who are not participating in this study, and redacted clinical study reports and other summary reports will be provided upon request (see Section 8.4 for more details). For more information, refer to the Roche Global Policy on Sharing of Clinical Trials Data at the following website:

[http://www.roche.com/roche\\_global\\_policy\\_on\\_sharing\\_of\\_clinical\\_study\\_information.pdf](http://www.roche.com/roche_global_policy_on_sharing_of_clinical_study_information.pdf)

The results of this study may be published or presented at scientific congresses. For all clinical studies in patients involving an IMP for which a marketing authorization application has been filed or approved in any country, the Sponsor aims to submit a journal manuscript reporting primary clinical study results within 6 months after the availability of the respective CSR. In addition, for all clinical studies in patients involving an IMP for which a marketing authorization application has been filed or approved in any country, the Sponsor aims to publish results from analyses of additional endpoints and exploratory data that are clinically meaningful and statistically sound.

The investigator must agree to submit all manuscripts or abstracts to the Sponsor prior to submission for publication or presentation. This allows the Sponsor to protect proprietary information and to provide comments based on information from other studies that may not yet be available to the investigator.

In accordance with standard editorial and ethical practice, the Sponsor will generally support publication of multicenter studies only in their entirety and not as individual center data. In this case, a coordinating investigator will be designated by mutual agreement.

Authorship will be determined by mutual agreement and in line with International Committee of Medical Journal Editors authorship requirements. Any formal publication of the study in which contribution of Sponsor personnel exceeded that of conventional monitoring will be considered as a joint publication by the investigator and the appropriate Sponsor personnel.

Any inventions and resulting patents, improvements, and/or know-how originating from the use of data from this study will become and remain the exclusive and unburdened property of the Sponsor, except where agreed otherwise.

## **9.6            PROTOCOL AMENDMENTS**

Any protocol amendments will be prepared by the Sponsor. Protocol amendments will be submitted to the IRB/EC and to regulatory authorities in accordance with local regulatory requirements.

Approval must be obtained from the IRB/EC and regulatory authorities (as locally required) before implementation of any changes, except for changes necessary to eliminate an immediate hazard to patients or changes that involve logistical or administrative aspects only (e.g., change in Medical Monitor or contact information).

## Appendix 1 Schedule of Activities

	Screening a	Treatment (Each cycle=21 days)	Treatment Discontinuation (≤30 Days) b	Safety Visit c (120 Days ±30 Days)	Study Termination d
	Days -28 to -1	Day 1 (± 3 Days for Cycles ≥2)			
Informed consent a	x				
Medical, surgical, and cancer histories and baseline conditions, including demographic information e	x				
Viral serology f	x				
Concomitant medications g	x	x	x		
Opiate analgesics use for cancer pain h	x	x			
Tumor assessment i	x	Every 9 weeks (±3 days) for the first 27 weeks and every 12 weeks (±6 days) thereafter until confirmed radiographic disease progression, death, or loss of follow-up			
Complete physical examination j	x		x		
Limited physical examination k		x l		x	
ECOG performance status	x	x l	x	x	
Vital signs m	x	x			
Electrocardiogram n	x	x n	x		
Echocardiogram n	x				
Weight	x		x	x	
Height	x				
Hematology o	x	x l	x	x	
Serum chemistry p	x	x l	x	x	

## Appendix 1 Schedule of Activities (cont.)

	Screening a	Treatment (Each Cycle = 21 days)	Treatment Discontinuation (≤ 30 Days) b	Safety Visit c (120 Days ± 30 Days)	Study Termination d
	Days -28 to -1	Day 1 (± 3 Days for Cycles ≥ 2)			
Coagulation panel (INR, and aPTT or PTT) q	x		x	x	
TSH, free T3, free T4 r	x	x l	x	x	
Autoantibody testing	x				
Testosterone	x				
Historic values for PSA velocity s	x				
PSA t	x	x	x	x t	x t
Archival and/or fresh FFPE tumor tissue specimen or 15 unstained slides u	x				
Tumor biopsy v		At the time of confirmed radiographic progression			

## Appendix 1 Schedule of Activities (cont.)

	Screening a	Treatment (Each Cycle = 21 days)	Treatment Discontinuation (≤ 30 Days) b	Safety Visit c (120 Days ± 30 Days)	Study Termination d
	Days -28 to -1	Day 1 (± 3 Days for Cycles ≥ 2)			
Symptomatic skeletal events w			x		
Atezolizumab infusion x		x			
Enzalutamide treatment y		x			
Adverse events z	x		x		
Survival and anti-cancer therapy follow-up d				x	x

ECOG = Eastern Cooperative Oncology Group; eCRF = electronic Case Report Form; FFPE = formalin fixed paraffin embedded; HBcAb = hepatitis B core antibody; HBsAb = hepatitis B surface antibody; HBsAg = hepatitis B surface antigen; HBV = hepatitis B virus; HCV = hepatitis C virus; IV = intravenous; PCWG3 = Prostate Cancer Working Group 3; PD-L1 = programmed death-ligand 1; RECIST = Response Evaluation Criteria in Solid Tumors; SSE = symptomatic skeletal event; T3 = triiodothyronine; T4 = thyroxine; TSH = thyroid-stimulating hormone.

Notes: Assessments scheduled on the days of study treatment infusions should be performed before the infusion unless otherwise noted.

- a Written informed consent is required for performing any study-specific tests or procedures. Signing of the Informed Consent Form can occur outside the 28-day screening period. Results of standard-of-care tests or examinations performed prior to obtaining informed consent and within 28 days prior to study entry (except where otherwise specified) may be used for screening assessments rather than repeating such tests. If re-screening is required, then HBV, HCV, HIV, and autoantibody testing from the initial screening may be acceptable for screening assessment if performed < 60 days from Cycle 1 Day 1.
- b Patients will be asked to return to the clinic not more than 30 days after the last study treatment for a treatment discontinuation visit.
- c Patients will be asked to return to the clinic 120 days ± 30 days after the last study treatment for a safety visit. Only patients taking atezolizumab are required to return for the safety visit.
- d All patients will be followed for survival until study termination unless the patient requests to be withdrawn from the study; this request must be documented in the source documents and signed by the investigator. If the patient withdraws from the study, the study staff may use a public information source (e.g., county records) to obtain information about survival status only.
- e Cancer history includes stage, date of diagnosis, and prior anti-tumor treatment. Demographic information includes age, sex, and self-reported race/ethnicity. Smoking history should also be captured.

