- Absence of symptoms and signs indicating unequivocal progression of disease
- No decline in ECOG performance status that can be attributed to disease progression
- Absence of tumor progression at critical anatomical sites (e.g., leptomeningeal disease) that cannot be managed and stabilized by protocol-allowed medical interventions
- Written consent to acknowledge deferring other treatment options in favor of continuing study treatment at the time of initial disease progression

No crossover will be allowed from the control arm to the experimental arm.

Patients with rising PSA levels only (i.e., in the absence of confirmed radiographic or clinical progression) should continue to receive study treatment per PCWG3 criteria and recommendations (Scher et al. 2016). PSA rise without evidence of confirmed radiographic progression or a symptomatic skeletal-related event is strongly discouraged as a criterion to start a new systemic anti-neoplastic therapy during the first 12 weeks of therapy and is discouraged as a criterion to start a new systemic anti-neoplastic therapy throughout the study.

Focal palliative radiography (e.g., external-beam radiotherapy to address single sites of disease), initiation of bisphosphonates or denosumab, standard-of-care corticosteroid use of no greater than the equivalent of 10 mg of prednisone or prednisolone per day and pain management are allowed and should not result in discontinuation of study treatment. However, patients should be evaluated for clinically apparent SSE.

Initiation of radium-223 dichloride to manage symptomatic bone lesions is not permitted during study treatment.

Patients will undergo scheduled tumor assessments at baseline and every 9 weeks ( $\pm 3$  days) for the first 27 weeks and every 12 weeks ( $\pm 6$  days) thereafter until confirmed radiographic disease progression per PCWG3. In the absence of confirmed radiographic progression, tumor assessments should continue, regardless of whether patients start new anti-cancer therapy, until death, loss of follow-up, withdrawal of consent, or study termination by the Sponsor, whichever occurs first. For patients who continue to receive study treatment following confirmed disease progression, assessments will continue until loss of clinical benefit.

All primary imaging data used for tumor assessments may be collected by the Sponsor to enable the possibility of a centralized, independent review of response endpoints by an Independent Review Facility (IRF).

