#### **6.4.2            Secondary Efficacy Endpoints**

Analyses of the primary endpoint of OS and the key secondary efficacy endpoints listed below will be performed in a hierarchical fashion with type 1 error control (see Section 6.8.1). The primary endpoint of OS will be analyzed first. If the null hypothesis for the OS endpoint is rejected, then the key secondary endpoints will be in the order provided:

1. Time to cancer-related pain progression
2. Time to first symptomatic skeletal event (SSE)
3. rPFS

If for one endpoint in this list the null hypothesis cannot be rejected, then the results for this and all following endpoints are not considered to be statistically significant. Analyses of other secondary endpoints of this study will be considered as descriptive in nature, and no formal hypothesis testing will be conducted.

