##### **6.4.2.1        Radiographic PFS and Other Time-to-Event Endpoints**

The following secondary time -to -event endpoints will be analyzed using similar methods as those described for OS above:

- Time to cancer-related pain progression
- Time to first SSE
- rPFS
- Immune-modified rPFS
- Time to initiation or increased opiate analgesic use for cancer pain
- Time to PSA progression

Data for patients who do not have post-baseline information will be censored at the date of randomization plus 1 day. Data for patients who have not experienced an event at the time of the analysis will be censored at the last available assessment.

Hazard ratios and 95% CI from a stratified Cox proportional hazards model will be provided. Kaplan-Meier methodology will be used to estimate median time to event and the 95% CI will be provided. Analyses of rPFS will also include the rPFS rate at 6 and 12 months.

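### As the text reads, no symptomatic skeletal events are scheduled for collection after the discontinuation visit, although time to first SSE is an alpha-controlled endpoint in all randomized patients

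*Combined protocol and SAP*

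**What the plan says.** **Endpoint.** Section 6.4.2 lists "Time to first symptomatic skeletal event (SSE" second of three key secondary endpoints, after pain progression and before rPFS. Section 6.8.1 places all three in a hierarchy that holds overall type I error at 0.05. Section 6.4.2.1 analyses the endpoint by the OS methods, and data for patients without an event "will be censored at the last available assessment". Nothing there limits it to the treatment period.

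**Definition.** Table 1 and Appendix 1 count four kinds of event: radiation to relieve skeletal symptoms (including starting radium-223), symptomatic pathologic fracture, spinal cord compression, and tumor-related orthopedic surgery. On radium-223, Section 3.1 adds: "Initiation of radium-223 dichloride to manage symptomatic bone lesions is not permitted during study treatment".

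**Collection.** In Appendix 1 the row "Symptomatic skeletal events" has a single mark, read under the treatment discontinuation column; its footnote defines an SSE and gives no collection period. On that visit: "Patients will be asked to return to the clinic not more than 30 days after the last study treatment for a treatment discontinuation visit". The row "Survival and anti-cancer therapy follow-up" is marked at the safety visit and at study termination, and its footnote says: "All patients will be followed for survival until study termination unless the patient requests to be withdrawn from the study". On the safety visit, 120 days (±30) after last treatment: "Only patients taking atezolizumab are required to return for the safety visit".

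**The concern.** An endpoint measured from randomization in every randomized patient needs events collected until the first event, death or the end of the study. If collection ends near treatment stop, patients without an event are censored at about that time. Section 4.6.1 makes radiographic progression and symptomatic deterioration reasons for stopping, and both are plausibly linked to skeletal risk. Three things are then at stake:

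- a sizeable share of first events is not observed;
- the SSE-free curve is too high if risk rises after stopping;
- a difference between arms in time on treatment, or in attendance at the safety visit, can enter the comparison.

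SSE is also a component of the exploratory modified PFS, which would inherit the same gap.

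**Working it through.** **1. Is there another collection route after the discontinuation visit?**

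- *Sections 3.1 and 4.6.1* ask that patients be evaluated for SSE when palliative measures are used during treatment. They set no later contact.
- *Adverse event reporting (Section 5.3.1)* ends at 30 days for all events, and at 90 days for serious events and events of special interest. Both end sooner if new systemic therapy starts. Section 5.3.5.10 excludes events clearly consistent with progression, and Section 5.3.5.11 exempts hospitalization due solely to progression. A pathologic fracture or cord compression after progression can therefore go unreported.
- *After that window*, Section 5.6 specifies the long-term survival form for deaths.
- *Anti-cancer therapy follow-up* helps in part. Section 4.4.4 counts radiotherapy, including radium-223, as therapy intended to treat cancer, so a later start would probably be recorded. Its symptomatic purpose, and hence its status as an SSE, might not be.

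This leaves fracture, cord compression and orthopedic surgery without a reliable route.

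**2. The plan's own figures.** The documents give no SSE rate, event count or power. The OS figures reproduce. With 540 events and HR 0.72, power is Φ(0.3285 × √540 / 2 − 1.960) = Φ(1.857) = 96.8%, or 96.6% with the interim, against 97% stated. The final boundary is exp(−2 × 2.025 / √540) = 0.840, against 0.84. Neither bears on SSE.

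**3. Share of first SSEs after the visit, using medians quoted in the background sections.** These are proxies, not trial values:

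- time on treatment 3 months (PFS) or 8.1 months (rPFS), both from Section 1.1.2;
- time to first skeletal event 9.8 or 15.6 months (the radium-223 trial, Section 1.1.1);
- OS 12 or 16.7 months (Section 6.1).

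Take independent exponential times with rates μ (stopping), λ (SSE) and δ (death), each ln 2 / median, and a window w = 30/30.44 = 0.986 months. Without an administrative cut-off:

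share = exp(−(λ+δ)w) × μ / (μ+λ+δ)

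- Low end (8.1, 9.8, 12): μ = 0.0856, λ+δ = 0.1285; 0.881 × 0.400 = 0.352.
- High end (3, 15.6, 16.7): μ = 0.2310, λ+δ = 0.0859; 0.919 × 0.729 = 0.670.

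Simulation with 13-month accrual and a cut at Month 38 gives slightly lower values:

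| Treatment (months) | SSE | OS | First SSEs per 720 | Later than 30 days | Later than 120 days |
|---|---|---|---|---|---|
| 3 | 9.8 | 12 | 389 | 55.7% | 37.5% |
| 3 | 9.8 | 16.7 | 440 | 59.0% | 41.4% |
| 3 | 15.6 | 12 | 300 | 61.1% | 44.0% |
| 3 | 15.6 | 16.7 | 346 | 64.5% | 48.3% |
| 8.1 | 9.8 | 12 | 389 | 34.1% | 22.8% |
| 8.1 | 9.8 | 16.7 | 440 | 36.9% | 25.6% |
| 8.1 | 15.6 | 12 | 300 | 38.7% | 27.6% |
| 8.1 | 15.6 | 16.7 | 346 | 42.0% | 31.0% |

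**4. Wider assumptions.** Here the SSE median on treatment is 15 to 25 months, the hazard is unchanged or doubled after stopping, the death median is 14 months, time on treatment is 3, 6 or 8.1 months, and collection ends one month after stopping. The share missed runs from 40% (8.1 months, unchanged hazard, SSE median 15) to 72% (3 months, doubled hazard, SSE median 25). In one setting (6 months, doubled, 25), 126 of 312 first SSEs among 720 patients are collected, so 1 − 126/312 = 60% are missed.

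**5. Effect on the curve at 12 months, SSE median 20.**

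| Median time on treatment | True, hazard doubled | Reported |
|---|---|---|
| 3 months | 50.5% | 61.0% |
| 6 months | 54.8% | 62.9% |
| 8.1 months | 57.0% | 63.8% |

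With an unchanged hazard and independent stopping, both curves equal 2^(−12/20) = 66%. Events are lost but the curve is not biased.

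**The case against.** The strongest objection is that the mark in the SSE row cannot be trusted. The adverse events row has the same layout, with no mark under treatment, yet its footnote and Section 5.3.1 require collection throughout treatment and, for serious events, to 90 days. The SSE mark is therefore probably a merged cell whose right-hand limit is lost. Where collection does stop at discontinuation, for tumor assessments and PSA, the footnotes say so; the SSE footnote does not. This stands against any claim that SSE collection was deliberately ended, and a reader who infers that goes beyond the text. It does not supply a collection period, and an extension only to the safety visit would make ascertainment differ by arm.

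A reader might also infer that radium-223, barred on treatment, can never be counted. The documents do not support that: the anti-cancer therapy follow-up would probably record it. The open question is whether it would be classified as an SSE.

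Third, this is a close-out version. Sections 3.3, 4.5.6 and 4.5.8 record closure for futility and the end of central laboratory and PRO collection. SSE is tested only after OS and then pain progression succeed, so a confirmatory test is unlikely. Schedules in force earlier in the trial are not visible, and Section 4.5.8 still mentions long-term follow-up. The simulated counts apply one schedule to everyone and cannot be read as this trial's losses. All of this stands and limits the practical weight of the point.

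**Conclusion.** The point holds as a gap between endpoint and schedule. The documents state no SSE collection period beyond the discontinuation visit, while the endpoint is defined in all randomized patients and kept in the alpha-controlled hierarchy. Censoring near treatment stop is an inference from that schedule; the plan itself names only the last available assessment.

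About one third to 70% of first SSEs would fall after the visit (34% to 65% with the background medians, 40% to 72% with the wider set). This rests on exponential times and on PFS figures standing in for time on treatment, although treatment beyond progression is allowed. Two stronger readings are not supported. That most events are lost is true over only part of the range. That the curve is too favourable needs a link between stopping and skeletal risk, and the doubled hazard is an assumption with no source in the documents. No bias in the hazard ratio was computed, so neither its direction nor its size can be claimed. The change is worth making but is not critical in a study that is closing.

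**What to change.** Add first SSE (type and date) to the survival and anti-cancer therapy follow-up contact, identically in both arms, until first SSE, death or study termination. State that period in the SSE footnote of Appendix 1.

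If close-out prevents this, state in Appendix 1 and Section 6.4.2.1 that SSEs are collected only to the discontinuation visit, censor both arms at that same point, and report a descriptive on-treatment endpoint removed from the Section 6.4.2 hierarchy.

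The cost is one question at contacts already planned and one eCRF field, or one paragraph in the analysis plan. With the study closing for futility, the gain is mainly that any reported SSE curve or hazard ratio says clearly what it measures.
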